To inform our sample size calculations, we used a conservative estimate of the average number of index TB patients of 11 per clinic per 8-week block period (g), assuming a rho-alpha of 0.172 and rho-beta of 0.647 from our preliminary data, and an average number of symptomatic contacts per index TB case (m) of 1, as well as a pre-intervention proportion of patients completing treatment (p1) of 0.4, a post-intervention proportion of treatment completion (p2) of 0.6, the number of clusters crossing at each step (k) of 2, and total steps (steps) of 6.

Using the Stata command:

steppedwedgeTwoLevelsD, binomial complete(1) vartotal(1) p1(0.4) p2(0.6) m(1) k(2) rho(0.172) rho2(0.647) alpha(0.05) steps(6) g(11),

We estimate that the trial will conservatively need 924 total symptomatic contacts of index TB patients to achieve a power of 99%. Sample size estimates were reached using PASS 15 and Stata 16, with an extension to account for multiple levels of clustering as per Hemming et al.[3] and Davis-Plourde [4]. Although some sample size estimators predict 100% power, 100% power is not theoretically achievable, and therefore rendered as 99%. Because index patients and contacts are participants in routine services, we will not limit enrollment if it exceeds these numbers, which we project may be higher by four-fold or greater if the intervention strategy is highly effective.

Tests for Two Proportions in a Stepped-Wedge Cluster-Randomized Design

Design type: Complete

Test statistic: Wald Z-Test

$H_0: P_1 - P_2 = 0$.

$H_A: P_1 - P_2 = D_1 \neq 0$.

ICC (intra-cluster correlation coefficient (rho)) measures the correlation of observations within a group/cluster. It indicates the dependency of observations on the group/cluster they belong to. Mathematically, it is calculated as the variance between groups/clusters divided by the total variance (which is variance between groups plus variance within groups). Thus, the higher the correlation within the groups (meaning less variability within groups/clusters), the lower the variance within groups leading to a higher ICC. The converse is also true, in that the lower the correlation within groups (meaning less variability within groups/clusters), the higher the variance within groups leading to a lower ICC.

Table 2: Power and sample size (total number of symptomatic contacts of index TB patients) estimation

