Clusters S/T/k/K	Sample size m/g	Control (P1)	Intvnt (P2)	(D1)	Rho alpha (rho)	Rho beta (rho2)	Alpha	Symptomatic contacts (N)	Design power
6/7/2/12	1/11	0.20	0.40	0.20	0.172	0.647	0.05	924	1.0000
6/7/2/12	1/11	0.20	0.45	0.25	0.172	0.647	0.05	924	1.0000
6/7/2/12	1/11	0.25	0.45	0.20	0.172	0.647	0.05	924	1.0000
6/7/2/12	1/11	0.25	0.50	0.25	0.172	0.647	0.05	924	1.0000
5/6/2/10	1/11	0.20	0.40	0.20	0.172	0.647	0.05	660	1.0000
5/6/2/10	1/11	0.20	0.45	0.25	0.172	0.647	0.05	660	1.0000
5/6/2/10	1/11	0.25	0.45	0.20	0.172	0.647	0.05	660	0.9999
5/6/2/10	1/11	0.25	0.50	0.25	0.172	0.647	0.05	660	1.0000
4/5/2/8	1/11	0.20	0.40	0.20	0.172	0.647	0.05	440	0.9983
4/5/2/8	1/11	0.20	0.45	0.25	0.172	0.647	0.05	440	1.0000
4/5/2/8	1/11	0.25	0.45	0.20	0.172	0.647	0.05	440	0.9948
4/5/2/8	1/11	0.25	0.50	0.25	0.172	0.647	0.05	440	0.9999

Definitions

S is the number of steps in the study design. $S = T - 1$.

T is the number of time periods in the study, including the baseline. $T = S + 1$

k is the number of clusters switching from control to treatment at each step.

K is the total number of clusters to be randomized.

m is the average number of contacts per index TB patient per 2-month block period.

g is the average number of index TB patients per 2-months block period

N is the total sample size of contacts from all index TB patients, clusters and time periods combined. $N = m^*g^*T^*K$.

P1 is the control/baseline proportion.

P2 is the treatment proportion, assuming the alternative hypothesis.

D1 = $P2 - P1$ is the difference assuming the alternative hypothesis (H_A).

Rho-alpha (rho) is the ICC level 1 for index TB patients nested in clinics

Rho-beta (rho2) is the ICC level 2 for contacts nested in index TB patients

Alpha is the probability of rejecting the null hypothesis when it is true.

Summary

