If we power for a minimum detectable difference of 0.20, a sample of 12 clinics/clusters in a complete stepped-wedge cluster-randomized design with 7 time periods (including the baseline), 6 steps, 2 clusters switching from pre-intervention (control) to post-intervention (treatment) at each step, two levels of ICC (rho-alpha of 0.172 and rho-beta of 0.647 from our pre-trial data), an average of 11 index TB patients per cluster per 2-months' time period, a minimum of 1 symptomatic contact per index TB patient, a total number of index TB patients needed for the trial is 924 which achieves 99% power for a minimum detectable proportion difference of 0.1 between a pre-intervention proportion of 0.2 and a post-intervention proportion of 0.4.

These and other sample size estimates are indicated under Scenario 1 in Table 2, in the upper panel in bold, black font.

We also are proposing sample size calculations for other contingencies. Specifically, we wish to plan for scenarios in which one or both sites in a paired-site cluster do not achieve the expected number of symptomatic contacts patients due to secular events, the whole pair will be excluded from the final analysis. Given the effect of a small number of clusters on the power of SWTs, we see two plausible scenarios namely:

- i. Scenario 2: One pair of clusters is excluded from the final analysis. In this case, the number of steps reduces to 5, the time periods reduce to 6 and the number of clusters reduces to 10. The power estimates for this scenario are presented in Table 2 above, in the middle panel in blue ink.
- ii. Scenario 3: Two pairs of clusters are excluded from the final analysis. In this case, the number of steps reduces to 4, the time periods reduce to 5 and the number of clusters reduces to 8. The power estimates for this scenario are presented in Table 2 above, in the lower panel in purple ink. This is the worst-case scenario. The estimates indicate that this scenario would have 99.8% for a minimum detectable proportion difference of 0.2 between a pre-intervention proportion of 0.2 and a post-intervention proportion of 0.4.

Blinding

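### Scenarios 2 and 3 drop trial periods that no rule drops, so N = 660 and 440 are wrong; the 99.8% worst-case power also fails, but for two other reasons

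*SAP*

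**What the plan says.** The Summary under Power and sample size calculation in the SAP plans for pairs of sites that recruit too few symptomatic contacts because of secular events; such a pair leaves the final analysis entirely. For one lost pair (Scenario 2) the steps fall to 5, and "the time periods reduce to 6 and the number of clusters reduces to 10". For two lost pairs (Scenario 3), "the number of steps reduces to 4, the time periods reduce to 5 and the number of clusters reduces to 8". Table 2 gives N = 660 and 440 for these layouts. For 0.20 versus 0.40 it gives power 1.0000 and 0.9983, and the text calls Scenario 3 the worst case, with 99.8%.

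The inputs are "assuming a rho-alpha of 0.172 and rho-beta of 0.647 from our preliminary data", 11 index patients per clinic per 8-week block, and "average number of symptomatic contacts per index TB case (m) of 1". The Definitions state that "N is the total sample size of contacts from all index TB patients, clusters and time periods combined", with N = m × g × T × K and T = S + 1. The design type is given as complete, with "Test statistic: Wald Z-Test" and a two-sided alternative.

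Elsewhere, SAP Randomization fixes the crossovers two months apart, starting in month 3. SAP Trial Design drops data by date only for the transition blocks and the pause, and promises at least 8 weeks of data after each transition.

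**The concern.** Excluding a pair removes rows from the design, not columns. The other clinics still recruit in every block, and the lost pair's crossover becomes a gap in the wedge. The SAP applies T = S + 1 mechanically and so computes shorter trials with evenly filled steps. The two sample sizes then do not belong to the analyses described, and a single power figure cannot show whether it matters which pairs go.

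This has practical weight. SAP Trial Design reports movement restrictions affecting Mubende and Kasambya, which Figure 2 places in Groups 1 and 4. Losing both groups is a concrete form of Scenario 3, and someone deciding whether to exclude them would look up the 99.8%.

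**Working it through.** **1. The SAP's sample sizes.** With m = 1 and g = 11, N = 11 × T × K. The stated values reproduce: 11 × 6 × 10 = 660 and 11 × 5 × 8 = 440.

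**2. The calendar.** One baseline block, six transition blocks in turn from month 3, and one block after the last transition make 8 two-month blocks. This agrees with the 16 months in the Protocol (Sample Size). Each clinic loses its own transition block and contributes 7. A complete 7-period layout also gives 7 per clinic. So N = 11 × 7 × 10 = 770 (110 more than stated) and 11 × 7 × 8 = 616 (176 more). On a 7-block calendar with the transition removed, N would be 11 × 6 × 10 = 660 and 11 × 6 × 8 = 528. But Group 6 would then have no data after transition, contrary to SAP Trial Design.

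**3. The SAP's power.** The model uses fixed period effects, a random clinic effect and cluster-period means. With σ² = P1(1 − P1), clinic variance τ² = rho × σ² and cluster-period noise s², the variance of the effect in a complete design is

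K s²(s² + Tτ²) / [(KU − W)s² + (U² + KTU − TW − KV)τ²].

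Here U is the number of treated clinic-periods, W the sum of squared period totals and V the sum of squared clinic totals. For 4 steps, 5 periods and 8 clinics: U = 20, W = 120, V = 60. With P1 = 0.20, σ² = 0.16 and τ² = 0.172 × 0.16 = 0.02752.

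Table 2 reproduces only with s² = (1 − rho2)σ²/g = 0.353 × 0.16/11 = 0.005135:

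- Variance = 8 × 0.005135 × 0.14273 / (40 × 0.005135 + 120 × 0.02752) = 0.005863/3.5078 = 0.001671, so SE = 0.0409.
- z = 0.20/0.0409 = 4.89, and power = Φ(4.89 − 1.96) = 0.9983, as stated. The same model returns 0.9948 for 0.25 versus 0.45.

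**4. Keep 7 periods and change nothing else.** Over all 15 choices of two lost pairs, power for 0.20 versus 0.40 is 99.96% to 99.995%. For 0.25 versus 0.45 it is 99.8% to 99.97% (stated 99.48%). Power rises because the SAP's layout is part of the real one: removing group d together with period d or d + 1 leaves exactly the 5-step layout.

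**5. Remove the transition cells, keeping the SAP's variance.** This is point (a). The clinic-level information matrices are summed by generalized least squares with each clinic's transition block missing.

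**6. Correct the noise term.** This is point (b). With m = 1, two contacts in the same clinic and block belong to different index patients, so they share only the clinic effect. The noise is therefore (1 − rho)σ²/g. The term (1 − rho2)σ²/g omits the variation between index patients. The ratio is 0.828/0.353 = 2.35. In the SAP's own 4-step layout, s² = 0.828 × 0.16/11 = 0.01204. The variance is then 8 × 0.01204 × 0.14964/(40 × 0.01204 + 120 × 0.02752) = 0.01442/3.7841 = 0.00381, SE = 0.0617, and power = Φ(3.24 − 1.96) = 90.0%.

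Results for 0.20 versus 0.40 (minimum to maximum over which pairs are lost):

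| Setting | One pair lost | Two pairs lost |
|---|---|---|
| SAP as stated | 1.0000 | 99.83% |
| 7 periods kept, complete, SAP noise | above 99.99% | 99.96% to 99.995% |
| (a) 8 blocks, transition removed, SAP noise | 99.9% to 99.99% | 97.8% to 99.9% |
| (a) and (b), variance at P1 (0.16) | 92.2% to 96.4% | 74.0% to 92.3% |
| (a) and (b), variance averaged, (0.16 + 0.24)/2 = 0.20 | 85.6% to 91.9% | 64.4% to 85.7% |

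For 0.25 versus 0.45, (a) alone gives 95.6% to 99.7% with two pairs lost. The two-pair minimum in row (a) is the loss of Groups 1 and 2 (SE 0.0504, z = 3.97); the maximum is the loss of Groups 3 and 5 (SE 0.0391, z = 5.11). Losing Groups 1 and 4 under (a) and (b) with averaged variance gives 80.7%.

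**The case against.** The best defence is that the slip errs on the safe side. That is right for power, and under either noise term. With (1 − rho)/g, averaged variance and a complete design, the SAP's 4-step layout gives 82.6%, while keeping 7 periods gives 87.6% to 93.5%. A reader might infer that the deleted periods inflate the 99.8%. They do not; points (a) and (b) lower it, and both apply to Scenario 1 as well.

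Two other inferences go too far. One is that the shortened layouts could never arise: they would if a full period of valid data from the retained clinics were also discarded, though the SAP plans no such thing. The other is that the SAP uses these power figures to justify excluding pairs. It names under-recruitment as the trigger and presents the scenarios as contingency planning.

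It can also be said that N is a planning minimum. The SAP does not cap enrolment, and its pre-trial data show 22.7 index patients per clinic per block against the 11 assumed. That makes the low power figures cautious, but it does not make 660 and 440 the right totals under the SAP's own inputs.

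Finally, the influence of which pairs are lost is small on the SAP's variance: under 0.1 point in a complete design and about 2 points with the transition removed. It reaches 18 to 21 points only with (a) and (b) together.

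**Conclusion.** The sample sizes for Scenarios 2 and 3 are wrong by the SAP's own formula: 770 and 616 instead of 660 and 440, given seven analysed blocks per clinic. This error does not overstate power.

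The 99.8% still cannot stand as a worst case. Discarding the transition data, which the SAP commits to, brings the two-pair minimum to 97.8% (95.6% for 0.25 versus 0.45). With the noise term that m = 1 requires, the minimum is 74.0%, or 64.4% with averaged variance.

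These figures assume 11 index patients per block, one symptomatic contact each, rho = 0.172, a clinic effect constant over time and 8 equal blocks. I have not modelled the pauses, which alter block lengths. Point (a) rests on the SAP's text. Point (b) rests on its inputs and on the only noise term found to reproduce Table 2.

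**What to change.** Recompute both scenarios on the actual calendar: keep every period, delete the rows of the lost pair or pairs, leave out the transition cells, and use (1 − rho)/g for the cluster-period noise. State the calendar and whether the variance is taken at P1 or averaged. In place of 660, 440 and 99.8%, report the resulting N (770 and 616 on the 8-block calendar) and the minimum and maximum power over which pairs are lost. Apply the same two corrections to Scenario 1 so that the three panels of Table 2 remain comparable.

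The cost is a short calculation and an SAP wording change, with no effect on conduct or data collection. The downside is that the stated power becomes less favourable.

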This sequence of allocation restricted by sites will be determined through a two-stage random drawing during a public randomization ceremony held in Kampala, Uganda. A senior clinician representative of each health center (e.g., the TB focal person), the Health Facility Administrator-in-Charge, and the District Health Officer will be invited to attend a public randomization ceremony chaired by the Uganda NTLP Director. In the first, so-called “Cluster Stage”, health facilities will be divided into high-volume and low-volume strata for cluster assignments. Each health center representative will draw, without replacement, one ball labeled with the cluster designation, until all sites are assigned in paired clusters. In the second and final, or “Group Stage,” the two representatives of each cluster will assign one representative to draw, without replacement, 1 of 6 balls (labeled 1, 2, 3, 4, 5, 6) from an opaque bag to choose the group. Group 1 will be the first group to cross over, Group 2 the second to cross over, and so on. The sites will follow this cross-over sequence at equally spaced, 2-month intervals during the trial period, starting at the beginning of month 3.

Statistical Methods

For standardization purposes, the start of effective intervention exposure for clusters will be considered the first Monday of the next calendar week after the end of each 8-week transition period. This standardization will help fix the trial period slices and improve statistical efficiency for the within-period analyses. We will use a cluster-period mixed-effects logit model[5, 6] to assess differences between post-intervention and pre-intervention periods with regard to the proportion of contacts who completed TB evaluation within 60 days of index treatment initiation, the proportion of contacts diagnosed with active TB, the proportion of contacts initiating TB preventative therapy and proportion of all TB cases among contacts. We will use a cluster-period mixed-effects Poisson model[5, 6] to assess the difference between post-intervention and pre-intervention periods with regard to the count of contacts diagnosed with active TB and the count of contacts initiated on TB preventative therapy within and between periods. We will test for secular trends using both fixed and random effects. If secular trends are present, we will use a segmented regression model.

a. Dataset assembly, cleaning, and creation of new variables

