Within-period analyses comprise period-specific assessments where aggregated outcomes of groups in the pre-intervention exposure are compared with those of groups receiving the intervention exposure during the same trial month(s). For between-period analyses, outcomes for each group are compared to those of the same group in the intervention versus pre-intervention exposures, *i.e.*, cluster-specific, control-intervention comparisons across different time periods. Post-baseline measures will include pre-intervention and intervention exposure since groups will enter intervention exposure at varying times. For clusters still in the control exposure period, each subsequent trial month after study month 2 before the commencement of their transition period will be analyzed as the pre-intervention, post-baseline period. The start of effective intervention exposure (*i.e.*, the post-transition period) for each group will be the first day of the calendar month following the 2nd month of the transition interval.

c. Intervention Effect Analysis

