where y_{ijk} is the outcome of individual k in period j from clinic i , μ is the mean outcome in the first period, β_j is the difference between period j and the first period with $\beta_1=0$, θ is the intervention effect, X_{ij} is 1 if cluster i received the intervention in period j and 0 otherwise, u_i is a random effect for cluster, and e_{ijk} is the within-cluster variability.

In a stepped wedge trial, the outcomes will be aggregated at cluster level hence the general model form will be

$$Y_t = \mu + \beta_j + \theta X_{ij} + u_i + e_{ijk}, \dots \quad \text{Equation 2}$$

where Y_t = aggregated outcome within each time slice t , calculated from Y_{ijk} (for i exposure, j period (month) and cluster k). We will adjust for unbalanced time-independent variables at baseline and confounders. The proportion of the outcome variable will be calculated for each site and cluster for each study time-exposure slice.

For between-period (horizontal) comparisons, comparative analysis is done at cluster level hence the general model form is:

$$\text{logit}(Y_{jt}) = \alpha + \beta x_{jt} + \sum \gamma_t z_t + u_j \dots \quad \text{Equation 3}$$

where j indexes the clusters, t indexes the steps, x_{jt} indicates a cluster and exposure; is coded 0 when the j th cluster is in pre-intervention (control) exposure and 1 when it is in the post-intervention (intervention); β represents the intervention effect, γ_t represents the time-specific effects, z_t the steps and u_j represents the cluster-level random effects (within-cluster correlation).

Within-period (vertical) comparisons are done by fitting a model as in Equation 4

$$\text{logit}(Y_{jt}) = \alpha + \beta x_{jt} + \sum \gamma_t z_t + u_j \dots \quad \text{Equation 4}$$

- where x_{jt} indicates a cluster and time and is coded 0 for clusters in pre-intervention (control) exposure and 1 for clusters in the post-intervention (intervention); β represents the intervention effect, and γ_t represents the time vertical slices.

Alternative Statistical analyses[§]

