3.1.2 Populations and subgroups to be analyzed

a. Populations

- **Intention-to-treat (ITT):** The primary analysis will consider the intention-to-treat population, including all index patients eligible at all sites and their identified and screened contacts. Pre-intervention patients in the intention-to-treat population will be those who were diagnosed at a site during the pre-intervention period, and subsequently, their contacts will be considered pre-intervention contacts. Intervention period patients in the ITT population will be those who were diagnosed with TB at a site during the intervention period, and subsequently, their contacts will be considered intervention contacts.
- A per-protocol analysis is not relevant in this case since all community health workers at the site during the intervention period will be exposed to the user-centered implementation strategy, and it is not possible to quantitatively measure adherence to the implementation components in the context of the pragmatic features of the trial.

b. **Adjusted analyses:** In the presence of secular trends (and thus analysis at the individual level), the adjusted analyses will consider age (continuous), sex, HIV status, and any other baseline characteristics found to be imbalanced between control and intervention periods. In the absence of secular trends (and thus aggregated analysis by site and by month), the adjusted analyses will consider covariates such as the proportion of male vs. female, mean age, health center level, health center location (peri-urban vs. rural), and GDP of health center district (low vs. high). Data will be collapsed by the sum of total outcomes for binary outcome variables and mean value for any continuous variables (e.g., age). We will adjust for trial period as appropriate for stepped wedge trial data analysis.

c. **Subgroup analyses:** In the case of individual patient data analysis, five subgroups will be analyzed using the ITT population.

- Age
- Sex: All eligible patients at randomized health centers will be divided into two groups by sex and analyzed separately.

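### An undefined secular-trend test chooses the model, the unit of analysis and part of the covariate set, and no sentence says that period terms stay if no trend is found

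*SAP*

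**What the plan says.** **Model.** SAP, Statistical Methods: "We will test for secular trends using both fixed and random effects. If secular trends are present, we will use a segmented regression model". No equation is given for the segmented model.

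**Unit and covariates.** SAP 3.1.2, item b, makes the same finding decide two more things:

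- Trend found: "In the presence of secular trends (and thus analysis at the individual level), the adjusted analyses will consider age", together with sex, HIV status and any imbalanced baseline characteristics.
- No trend found: "In the absence of secular trends (and thus aggregated analysis by site and by month), the adjusted analyses will consider covariates" such as sex mix, mean age, health centre level, location and district GDP.

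**Period terms.** The same item ends: "We will adjust for trial period as appropriate for stepped wedge trial data analysis". Equations 1–4 in the Intervention Effect Analysis section each contain a period or step effect. Equation 2 is introduced with "In a stepped wedge trial, the outcomes will be aggregated at cluster level hence the general model form will be", and its text adds "The proportion of the outcome variable will be calculated for each site and cluster for each study time-exposure slice".

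**Other text on the unit.** The Primary Outcome definition fixes an aggregate, cluster-level, exposure-specific measurement. The Intervention Effect Analysis section also aggregates outcomes at clinic level.

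**Protocol.** The mixed-effects logit model in Protocol section 13 has random effects for clustering and fixed effects for step, with no preliminary trend test. The SAP Overview gives the SAP precedence where the two differ.

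**The concern.** In a stepped wedge, every clinic's intervention time follows its control time, so calendar time is confounded with the intervention by design. The usual safeguard is to keep period effects in the model whatever the data show. Here a preliminary test decides the model, the level of the data and which covariates enter. Because its form and level are not given, two analysts who follow the SAP faithfully could run different analyses of the primary outcome.

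The two rules are also not joined up. Statistical Methods speaks of segmented regression and 3.1.2 of individual-level data, and nothing says whether these are one analysis. The individual-level branch sits badly with a primary outcome defined at cluster level.

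Time is not a remote worry in this trial: the Alternative Statistical analyses section itself describes high uncertainty about Ebola and other secular effects.

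**Working it through.** **1. The two branches side by side**

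| | Trend found | No trend found |
|---|---|---|
| Model | segmented regression, no equation | cluster-period mixed model (Equations 2–3) |
| Unit | individual | site by month |
| Covariates named in this branch only | HIV status, imbalanced baseline characteristics | centre level, location, district GDP |
| Fits the cluster-level primary outcome | no | yes |

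Age and sex appear in both branches, in different forms.

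**2. Does the plan's power already include period effects?** Inputs from the SAP power section: ρ = 0.172, ρ₂ = 0.647, 11 symptomatic contacts per clinic-period, two-sided α = 0.05. The Hussey–Hughes formula, which has fixed period effects and a random clinic effect, is

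Var = Iσ²(σ² + Tτ²) / [(IU − W)σ² + (U² + ITU − TW − IV)τ²],

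with τ² = ρ·p₁(1 − p₁) and σ² = (1 − ρ₂)·p₁(1 − p₁)/11. I is the number of clinics and T the number of periods. U is the number of intervention cells. W and V are the sums of squared column and row totals of the design matrix.

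For 8 clinics, 0.20 to 0.40: T = 5, U = 20, W = 120, V = 60, σ² = 0.353 × 0.16/11 = 0.005135, τ² = 0.172 × 0.16 = 0.02752.

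Var = 8 × 0.005135 × 0.14273 / (40 × 0.005135 + 120 × 0.02752) = 0.001671, so SE = 0.0409.

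Power = Φ(0.20/0.0409 − 1.96) = Φ(2.93) = 0.9983, as in Table 2.

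The same formula reproduces all 12 powers in Table 2 to four decimals, and N = 1 × 11 × 7 × 12 = 924. I reproduce this variance split here without endorsing it. The point is only that period effects are already in it.

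**3. Does the unstated test form matter?** Simulation with no intervention effect: 12 clinics, 11 binary outcomes per clinic-period, mean 0.20, ICC 0.172, 20,000 runs per setting. The pre-test is at 5% and includes the intervention indicator. The rise of 10 points over the trial is assumed; the documents give no trend size.

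| | Complete, 7 periods | Transition removed, 8 periods |
|---|---|---|
| Joint period test finds the trend | 16.7% | 12.2% |
| Linear test finds the trend | 37.6% | 28.9% |
| The two tests disagree | 27.2% | 23.8% |

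With no trend they disagree in about 7% of trials. None of this assumes that period terms are dropped.

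**4. Natural reading: period terms kept.** Type I error is 4.6–5.1% for rises from 0 to 20 points in both layouts. Where time was kept in every branch, as linear time plus a level change after a positive test, it was about 3–8% over several assumed trend shapes.

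**5. Conditional illustration: no-trend branch without period terms.** The effect is then the within-clinic difference between intervention and control means. For a clinic with g control periods, the mean time gap is:

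- complete: (g + 8)/2 − (g + 1)/2 = 3.5 periods, so a share of 3.5/6 = 0.583 of a linear rise;
- transition removed: (g + 10)/2 − (g + 1)/2 = 4.5 periods, so a share of 4.5/7 = 0.643.

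With a random clinic effect (ICC 0.172) and 11 or 23 contacts per clinic-period, the shares are 0.573/0.578 and 0.634/0.638. A 10-point rise thus gives a spurious effect of about 6 points. Type I error after the 5% pre-test in step 3 is 42.0% (joint) or 32.5% (linear) in the complete layout, and 51.9% or 43.0% with transition removed. If the test leaves out the intervention indicator, separate mixed-model simulations of the same rise give much less, about 5–27%.

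**The case against.** The strongest reply is that the SAP never drops period terms. Equations 1–4 carry them without condition, and Equations 2 and 3 are the aggregated forms that fit the no-trend branch. The Statistical Methods section fixes time slices: "This standardization will help fix the trial period slices and improve statistical efficiency for the within-period analyses". The baseline and trend section adds: "Within-period analyses comprise period-specific assessments where aggregated outcomes of groups in the pre-intervention exposure are compared" within the same trial months. The commitment to adjust for trial period closes the very item that describes the no-trend branch. Its qualifier more naturally means in the manner this design requires than only if needed. A segmented model contains time by construction. The alternative xtlogit and xtreg models are a labelled contingency and are said to let aggregated data vary over time.

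All of this stands. A reader might infer from step 5 that the planned analysis has a type I error of a third to a half. The documents do not support that: those figures belong to a model the SAP does not write. A reader might also infer that keeping period terms costs power against the stated 99%. It does not, because Table 2 already includes them.

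It is also fair that item b is headed as adjusted analyses and uses permissive wording, so the covariate rule may not be meant for the primary estimate. But the Intervention Effect Analysis section says that the effect will be adjusted for potential confounders, and item b is where the covariates are named.

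The reply does not reach the choice of model and unit by a test that is not defined.

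**Conclusion.** The concern holds as a data-dependent choice of analysis, not as demonstrated error inflation. An undefined trend test selects the model, the unit and part of the covariate set. One of its branches conflicts with the cluster-level definition of the primary outcome, and the rule departs from the protocol's step-adjusted model, which has no pre-test.

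On the natural, period-adjusted reading, type I error is near nominal. What is lost is pre-specification: under an assumed 10-point rise, the choice between two ordinary tests changes the branch in about a quarter of trials.

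The remaining gap is that no sentence says the period terms stay when no trend is found. Only if they were dropped would 57–64% of a linear rise be credited to the intervention, with type I error of about 33–52% when the 5% pre-test includes the intervention indicator. Those figures rest on assumptions outside the documents: the size and linear shape of the trend, the form and level of the test, and the omission itself. The pauses in enrolment were not modelled. This should be fixed before analysis.

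**What to change.** - Name one primary model, following Equation 3 and Protocol section 13: the SAP's mixed-effects model with an intervention indicator, a clinic random effect and categorical fixed effects for period. Say that the period effects stay whatever any trend test shows.
- State the link now. If the rule for outcomes above 15% is kept, the control proportions of 0.20–0.25 in Table 2 point to the log-link Poisson model; otherwise state the logit.
- Fix one unit of analysis that agrees with the Primary Outcome definition, and one covariate set. Remove the two trend-dependent sentences from 3.1.2, item b.
- Make the trend test descriptive. Keep segmented regression and the models in the Alternative Statistical analyses section as sensitivity analyses, with period terms written out.

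The cost is SAP wording only. Period effects are already in the formula that reproduces Table 2, so the stated N of 924 and the stated power do not change.
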